Intervention: Eligible participants undergoing limb salvage procedures will be randomized to receive either TXA or placebo peri-operatively – one dose at initiation of surgical preparation and a second dose 6 hours after the first.

Brief Outline of Treatment Plan: The initial dose of tranexamic acid will be given at the initiation of surgical preparation. The second dose will be given 6 hours after the first dose (either intraoperatively or post-operatively). All doses will be given intravenously at 10 mg/kg with a maximum dose of 1 g. Doses will be double-blinded and randomized for each surgical procedure.

Study Design: Prospective Randomized Double-blind Control Trial (TXA versus placebo)

Sample Size: We estimate a total accrual of 39 limb salvage patients will be needed for the study to yield 38 evaluable subjects.

Data Management: Data management and statistical analysis will be provided locally by the Surgery Department and Biostatistics Department at St. Jude Children's Research Hospital.

Human Subjects Per Clinical Trials.gov, pediatric trials have reported minimal adverse events using TXA. Patients will be informed of this and other side effects during the informed consent discussion. Adverse events will be monitored and reported and treated appropriately.

CONTENTS

1.	OBJECTIVES	1
1.1	Primary Objective	1
1.2	Secondary Objectives	1
1.3	Exploratory Objectives	1
2.	BACKGROUND AND RATIONALE	2
2.1	Background	2
2.2	Rationale	3
2.3	Background and Rationale for Ancillary and Exploratory Studies	4
3.	RESEARCH PARTICIPANT ELIGIBILITY CRITERIA AND STUDY ENROLLMENT	5
3.1.	Inclusion Criteria	6
3.2.	Exclusion Criteria	7
3.3	Research Participant Recruitment and Screening	7
3.4.	Enrollment on Study at St. Jude	7
3.5.	Procedures for Identifying and Randomizing Research Participants	8
4.	TREATMENT PLAN	8
4.1	Study Treatment	8
4.2.	Dose Modifications	9
4.3.	Concomitant Therapy	10
4.4.	Supportive Care	10
5.	DRUG INFORMATION	11
5.1	Tranexamic Acid (Cykloapron®)	11
5.2	Placebo	12
5.3	Drug Management	12
6.	REQUIRED EVALUATIONS, TESTS, AND OBSERVATIONS	12
6.1.	Pre-Study Evaluations	12
6.2.	Evaluations During Therapy	13
6.3	Response Evaluations	16
6.4.	Off-Study Evaluations	16
6.5	Long-Term Follow-up Evaluations	16
7.	EVALUATION CRITERIA	16
7.1	Toxicity Evaluation Criteria	16
8.	CRITERIA FOR REMOVAL FROM PROTOCOL THERAPY AND OFF-STUDY CRITERIA	16
8.1.	Off-study criteria	16
9.	SAFETY AND ADVERSE EVENT REPORTING REQUIREMENTS	17

1. OBJECTIVES

1.1 Primary Objective

1.1.1. To evaluate the difference in intra-or post-operatively transfused blood volume (mL/kg) for patients undergoing limb salvage procedures of the distal femur or proximal tibia who are randomized to receive perioperative tranexamic acid (TXA) versus placebo.

- Study endpoint: intra- or post-operatively transfused blood volume (mL/kg), continuous measurement.

1.2 Secondary Objectives

1.2.1. To evaluate changes in platelets and in hemoglobin from pre-op to post-op level for patients randomized to receive perioperative TXA versus placebo.

- Study endpoint: changes in platelets and in hemoglobin from pre-op to post-op level, continuous measurement.

1.2.2 To evaluate differences in post-operative daily surgical drain output for patients randomized to receive perioperative TXA versus placebo.

- Study endpoint: postoperative daily surgical drain output, continuous measurement, for the duration of the drain.

1.2.3. To evaluate changes in estimated blood loss (EBL) for patients randomized to receive perioperative TXA versus placebo.

- Study endpoint: estimated blood loss, continuous measurement.

1.2.4. To evaluate the association between the intra-or post-operatively transfused blood volume and estimated blood loss (EBL) for patients randomized to receive perioperative TXA and placebo, respectively.

- Study endpoint: intra- or post-operatively transfused blood volume, continuous measurement, until resumption of chemotherapy; estimated blood loss (EBL), continuous measurement.

1.3 Exploratory Objectives

1.3.1. To evaluate differences in functional outcomes post-operatively for patients randomized to receive perioperative TXA versus placebo.

- Study endpoint: Functional Mobility Assessment (FMA), quality of life endpoints and Patient-Reported Outcomes Measurement Information System (PROMIS), quality of life endpoints.

1.3.2. To explore if significant correlations are observed between parameters reported with rotational thromboelastometry (ROTEM®) and EBL and transfusion requirements

in pediatric and young adult patients undergoing limb salvage procedure who are randomized to perioperative TXA versus placebo.

- Study endpoint: rotational thromboelastometry (ROTEM), continuous measurement; intra- or post-operatively transfused blood volume (mL/kg), continuous measurement; estimated blood loss (EBL), continuous measurement.

1.3.3. To evaluate differences in the prevalence and management of wound complications such as superficial or periprosthetic infections, wound dehiscence, contact dermatitis, post-operative hematomas, or any other clinically significant wound complication between patients randomized to receive perioperative TXA versus placebo.

- Study endpoint: Number of patients with the wound complications of interest.

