3.1. Inclusion Criteria

3.1.1. Participant undergoing limb salvage procedure of malignant bone tumor of the distal femur or proximal tibia, which typically requires blood transfusions.

3.1.2. Patient under the age of 25

3.1.3. Organ Function Requirements:

a. Adequate bone marrow function defined as:

- Upward trending peripheral absolute neutrophil count (ANC)
- Platelet count $\geq 100,000/\text{mm}^3$ (transfusion independent defined as no platelets required for 4 days)
- Hemoglobin $\geq 8.0 \text{ g/dL}$
- No RBC transfusion within 24 hours

b. Adequate renal function defined as:

- Creatinine clearance or radioisotope GFR $\geq 70 \text{ mL/min}/1.73\text{m}^2$
OR

Maximum Serum creatinine based on age/gender as follows: (threshold creatinine values were derived from the Schwartz formula for estimating GFR) (Schwartz GJ, Gauthier B. J Pediatr 1985; 106: 522-6)

Age	Maximum Serum Creatinine (mg/dL)	
	Male	Female
1 day to < 1 years	0.6	0.5
1 to < 2 years	0.6	0.6
2 to < 6 years	0.8	0.8
6 to < 10 years	1.0	1.0
10 to < 13 years	1.2	1.2
13 to < 16 years	1.5	1.4
≥ 16 years	1.7	1.4

c. Adequate liver function defined as:

- Total bilirubin $\leq 1.5 \times$ the institutional upper limit of normal (IULN) for age
- ALT (SGPT) and AST (SGOT) $\leq 2.5 \times$ IULN for age (or $< 5 \times$ IULN for patients with documented disease involving the liver or $10 \times$ IULN for patients receiving HDMTX)
- Serum albumin $> 2 \text{ g/dL}$

d. Adequate coagulation function as defined by International Normalized Ratio (INR) ≤ 1.5

3.1.4 Female participants of child-bearing potential (> 10 years old) must have a negative serum or urine pregnancy test within 72 hours of sedation

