11.4 Exploratory Objectives

11.4.1. To evaluate differences in functional outcomes post-operatively for patients randomized to receive perioperative TXA versus placebo.

Summary statistics will be provided for postoperative functional assessment scores (at each physical therapy session and at timepoints 6, 12, and 24 weeks) for each group. The group difference will be compared using two-sample t-test or Wilcoxon rank sum test, depending on the distribution of the observed data. Multiple comparison correction might be used for p-values to address the multiple testing issues due to measurements at multiple time points. We will calculate the missing proportions of the functional outcomes at every follow-up.

11.4.2. To explore if significant correlations are observed between parameters reported with rotational thromboelastometry (ROTEM®) and EBL and transfusion requirements in pediatric and young adult patients undergoing limb salvage procedure who are randomized to perioperative TXA versus placebo.

Multiple regression model is used to analyze the association between each measurement of rotational thromboelastometry (ROTEM®) and EBL and transfusion requirements while accounting for possible covariates. Multiple comparison correction might be used for p-values to address the multiple testing issues due to multiple measurements of ROTEM. Multivariate regression model may be used to study the associations between multiple measurements of ROTEM and EBL and transfusion requirements jointly. We will calculate the missing proportions of ROTEM at every follow-up.

11.4.3. To evaluate differences in the prevalence and management of wound complications such as superficial or periprosthetic infections, wound dehiscence, contact dermatitis, post-operative hematomas, or any other clinically significant wound complication between patients randomized to receive perioperative TXA versus placebo.

The proportions of observed wound complications and proportions of observed interventions will be estimated for both the TXA group and placebo group with 95% confidence intervals and compared between these two groups using Fisher's Exact Test. We will calculate the missing proportions of wound complications at

every follow-up. Multiple comparison correction might be used for p-values to address the multiple testing issues due to measurements at multiple time points.

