APPENDIX V: FUNCTIONAL ASSESSMENT

Functional Mobility Assessment (FMA) is a tool that was developed to measure functional mobility in children and adolescents with lower-extremity sarcoma. It is comprised of well-established outcome measures that examine various domains of function. The six categories tested by the FMA include pain, functional mobility, use of assistive devices, satisfaction with quality of gait, participation in the community, and endurance. 1.) Pain is measured by using a numeric scale requiring patients to rate any pain experienced in the prior week on a 0 (no pain) to 10 (worst pain imaginable) scale. 2.) Functional mobility will be measured by using the Timed Up and Down Stairs (TUDS) and Timed Up and Go (TUG). TUDS assesses the time required for a patient to walk up and down 12 stairs to measure functional mobility, balance, and motor skills. TUG measures the time needed to stand from a seated position, ambulate 3 meters, turn around, return to chair and resume sitting. This will provide a measure of dynamic balance and mobility. 3-5.) The use of supports, patient satisfaction, and participation in the community will be measured by patient provided responses to questions pertaining to the use of supports (brace, cane, crutches), satisfaction with walking quality, and participation in school, work, and/or sports. The responses will be scored on a 0-5 scale, with 0 demonstrating the least preferred outcome. 6.) A modification for the FMA will be implemented to measure endurance, which will be assessed using the 9-Minute Run-Walk Test. The patient will be instructed to walk or run for 9 minutes while trying to cover as much distance as possible. Heart rate (HR) and rate of perceived exertion (RPE) data will be collected during the walk/run. RPE measures the level of the patient's exertion using a likert scale of numbers (6-20) and adjectives describing effort. A wheeled feet counter will measure distance and a stopwatch will track time. Upon completion of the 9-minute run-walk, the physiological cost index (PCI) will be calculated by dividing the difference in the patient's heart rate (HR while walking- HR at rest) by walking speed in meters per minute. Marchese, et al.²⁰ reported that the FMA demonstrated good internal consistency as well as good construct validity in its ability to discriminate between patients with lower extremity malignancy and healthy controls.

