Patient-Reported Outcomes Measurement Information System (PROMIS) is a patient-reported outcome tool created by the National Institutes of Health (NIH), to establish a means of systematic outcome reporting for all patients across the health care spectrum.²¹ Due to its efficiency, reliability, and applicability to all patient types, the PROMIS continues to grow in popularity in many fields of medicine, including pediatrics, oncology, and orthopedics.²²⁻²⁵ It has shown good validity in both adult and pediatric populations, and is available in pediatric (ages 8-17), adult (ages 18 and older), and parent proxy (ages 5-17, or those unable to complete form independently) versions. The physical function domain of the PROMIS is intended to capture a patient's self-reported ability to perform daily activities, self-care, and athletic activities, and are subdivided into the areas of mobility and upper extremity. Additional domains utilized for this study include strength impact and pain interference. PROMIS forms will be provided to all patients enrolled on this study at the time of their functional assessment with adequate, allotted time for completion of questionnaires, and collection of forms at the end of assessment appointment.

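### Section 11.4.1 compares FMA and PROMIS without age, pre-op score or form version: the test is valid, but it gives up precision that could be had almost free

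*Combined protocol and SAP*

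**What the plan says.** - **Endpoints.** Section 1.3.1 lists "Functional Mobility Assessment (FMA), quality of life endpoints and Patient-Reported Outcomes Measurement Information System (PROMIS), quality of life endpoints".
- **Population.** Section 3.1.2 admits "Patient under the age of 25" and sets no lower age limit.
- **FMA.** Appendix V describes six categories. Two are performance tests: functional mobility (TUDS and TUG) and endurance (9-minute run-walk). For example, "TUDS assesses the time required for a patient to walk up and down 12 stairs". The other four (pain, supports, satisfaction with gait, participation) are patient-reported. No age norm is described.
- **PROMIS.** According to Appendix V it "is available in pediatric (ages 8-17), adult (ages 18 and older), and parent proxy (ages 5-17, or those unable to complete form independently) versions". No common scale is given, and no rule for combining versions or for choosing between self-report and proxy at ages 8-17.
- **Schedule.** Appendices I and VI place PROMIS pre-op and at 6 weeks, 3 months and 6 months. The FMA has the same post-operative visits but no pre-op assessment.
- **Analysis.** Section 11.4.1 states: "The group difference will be compared using two-sample t-test or Wilcoxon rank sum test, depending on the distribution of the observed data". It names no covariate. The ROTEM regression in 11.4.2, by contrast, is planned "while accounting for possible covariates".
- **Randomization.** Section 11.1 stratifies on pre-operative weight at 45.2 kg, not on age or PROMIS form.

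**The concern.** The same stairs, the same 3 metres and the same 9 minutes are set for young children and for patients of 24. If performance on them varies with age, the unadjusted test leaves that variation in the error term. The FMA has no pre-op value to absorb it, so age is the natural baseline variable. For PROMIS, scores from different instruments and respondents go into one comparison, and the scheduled pre-op score is left unused. Section 12.2 foresees participants turning 18 on study, so one patient's scores may also come from two versions. Weight-stratified randomization may partly balance age between the arms, but the planned test does not use the stratum.

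At stake is the precision of a small comparison. Section 2.2 gives better functional outcome as part of the reason for the trial.

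**Working it through.** **1. The plan's own figure.** The only powered endpoint is transfused volume (section 11.1): log(1+x) means 2.906 and 2.435, SDs 0.507 and 0.488, 19 per arm.

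- Difference = 2.906 − 2.435 = 0.471.
- Standard error = √[(0.507² + 0.488²)/19] = 0.161.
- Welch noncentral-t power is 0.810 at 19 per arm and 0.788 at 18.

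The stated 19 is reproduced and is not affected by this point. The plan states no SD, effect size or power for FMA or PROMIS, so everything below rests on assumed inputs.

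**2. Validity.** In simulation (20,000 runs, 19 per arm, form shifts of 0 to 1.5 SD, 30% or 50% of patients on the second form), the unadjusted t-test had type I error of 0.047-0.053. With randomization stratified on a weight variable that correlates 0.6-0.8 with age, and age explaining 20-40% of variance, it was 0.033-0.046. The test errs, if at all, on the conservative side.

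**3. Age and the FMA performance components.** Assumptions: a true difference of 0.8 total SD, all 38 patients observed, and age explaining a share R² of the variance.

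- Unadjusted: noncentrality 0.8 × √(19/2) = 2.466 with 36 df; power 0.67.
- Adjusted: noncentrality 2.466/√(1 − R²) with 35 df.
- Equivalent sample size: 38/(1 − R²).
- Standard error ratio, with an approximate allowance for the extra parameter: √[(1 − R²) × 36/35].

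| R² | Noncentrality | Adjusted power | SE ratio | Equivalent N |
|---|---|---|---|---|
| 0.05 | 2.530 | 0.69 | 0.99 | 40 |
| 0.10 | 2.599 | 0.71 | 0.96 | 42 |
| 0.20 | 2.757 | 0.76 | 0.91 | 47.5 |
| 0.40 | 3.183 | 0.87 | 0.79 | 63 |

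The power column takes age as balanced between arms. Putting the 36/35 allowance into the noncentrality as well lowers each power by about 0.01. By the same formula, adjustment breaks even at R² = 1 − 35/36 = 0.028.

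**4. PROMIS form.** Assumptions: half the patients on each of two forms, and form means that differ by δ within-form SDs. The between-form variance is 0.5 × 0.5 × δ² = δ²/4, so pooling multiplies the standard error by √(1 + δ²/4).

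| δ | SE factor | Power at 0.8 within-form SD (0.67 if δ = 0) |
|---|---|---|
| 0.3 | 1.011 | 0.66 |
| 0.5 | 1.031 | 0.64 |
| 1.0 | 1.118 | 0.57 |

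Only a full 1.0 SD shift makes the form effect material. The pre-op PROMIS score may be the more useful covariate, but the documents give no correlation from which to size it.

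**The case against.** **An unadjusted comparison of randomized arms is valid, and the objective is exploratory.** This stands. A reader might infer from the mixing of ages and forms that the false-positive rate rises. It does not, because randomization protects it (step 2).

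**The documents never say that timed performance depends on age.** This also stands. It is a plausible premise for fixed tasks across this age range. If the published FMA scoring already adjusts for age, the gain shrinks; Appendix V does not say.

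**The FMA is not wholly a performance measure.** Correct. The age argument reaches two of the six categories. A reader might extend it to the whole FMA, but Appendix V does not support that.

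**The inputs are chosen.** R² and the 0.8 SD difference have no anchor in the documents. At R² near 0.05 the gain is negligible, and the missing data that 11.4.1 anticipates would lower all the power figures.

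**Weight stratification already helps.** It may partly balance age. It does not remove age-related variance from the error term of a test that ignores it.

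**Should participants be kept on the form and respondent used pre-op?** A reader might infer this from the risk of a mid-study switch. The documents do not support it: Appendix V gives the pediatric form for ages 8-17, so holding an 18-year-old on it goes outside that range, and it would change the assessment procedure. Recording the version handles the matter at analysis.

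**Conclusion.** The point holds as a matter of precision only. Section 11.4.1 tests functional outcomes without age, pre-op PROMIS score or form version, although age bears plausibly on the FMA performance tasks and the plan itself describes different PROMIS forms.

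The gain for the FMA performance components runs from almost nothing (R² of 5%: power 0.67 to 0.69) to substantial (R² of 40%: 0.87). It depends wholly on an R² that the documents do not give. The PROMIS form effect is 1-3% of the standard error for shifts of 0.3-0.5 SD and 12% only at 1.0 SD. The documents give no ground for reading it as a serious distortion of the PROMIS comparison.

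This is a worthwhile refinement rather than a defect that threatens the trial. The primary analysis and the 19 per arm are untouched.

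**What to change.** In section 11.4.1:

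- **FMA performance components (TUDS, TUG, 9-minute run-walk).** At 6 weeks, 3 months and 6 months, compare the arms with a linear model containing arm, age at surgery and the weight stratum. Use the log scale or ranks if the data are skewed. The patient-rated categories can stay as planned.
- **PROMIS.** Compare the arms with a linear model containing arm, the pre-op PROMIS score and form version. Record the version (pediatric, adult or proxy) at every assessment and state how scores from different versions are placed on one scale. Report the version in use by arm, since a move to proxy after surgery could reflect the patient's condition.

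**Cost.** A few degrees of freedom: with 38 patients, the FMA model leaves 38 − 4 = 34 and the PROMIS model with three versions leaves 38 − 5 = 33, against 36 for the t-test. Age is known for every patient and pre-op PROMIS is already scheduled. The documents do not say that the form version is captured, so this may need one added data field as well as the analysis wording. No extra patients or visits are needed.

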2. BACKGROUND AND RATIONALE

2.1 Background

Limb salvage procedures in pediatric and young adult cancer patients are at high risk for perioperative bleeding with the resultant need of blood product transfusions. Limb salvage procedures may be performed at various anatomic sites with two of the most common sites being the distal femur and proximal tibia.

Perioperative bleeding can result in significant post-operative hematoma, which can affect wound healing and function. Additionally, platelet-derived growth factors are a vital part of the wound healing process. Thrombocytopenia secondary to perioperative blood loss contributes to wound healing complications. Delayed healing of wounds can adversely affect resumption of chemotherapy and rehabilitation. Patients with significant perioperative anemia requiring transfusion are more likely to be tachycardic, light-headed and unable to fully participate with rehab thus adversely affecting early mobilization and its benefits. The use of tranexamic acid has been shown to reduce the incidence of post-operative hematomas²⁷.

The use of antifibrinolytic drugs is one of the strategies for reducing perioperative blood loss. Antifibrinolytics such as aminocaproic acid, tranexamic acid, and aprotinin have been shown to reduce perioperative blood loss, autologous and/or allogenic blood transfusions, and associated costs in pediatric and adolescent patients who underwent major spinal, craniofacial or cardiac surgery¹⁻⁴. Since the restriction of aprotinin use in

2008, the most commonly used antifibrinolytic drugs have been the lysine analogs, tranexamic acid (TXA) and α -aminocaproic acid (EACA), which inhibit the conversion of plasminogen to plasmin and decrease the degree of fibrinolysis. These agents reduce perioperative blood loss by inhibition of clot breakdown⁵⁻⁷. Prospective, randomized studies have shown that the use of these agents in adults can be effective in reducing the perioperative blood loss and transfusion requirements in total joint arthroplasty and reconstructive surgery of the spine⁸⁻¹². In pediatric patients, the efficacy of antifibrinolitics such as TXA has been demonstrated in cardiac surgery, spine deformities surgery and craniofacial surgery^{1,2,13-15}. TXA is the most common antifibrinolytic used worldwide because EACA is not available in many countries¹.

Tranexamic acid (TXA) is FDA approved for pediatric and adult hemophilia patients for tooth extraction at 10 mg/kg/dose IV immediately before surgery, then 10 mg/kg/dose IV 3 to 4 times daily for 2 to 8 days. Randomized controlled trials and systematic reviews support the use of TXA to decrease blood loss and transfusion requirements in pediatric patients undergoing cardiac surgery, spine deformities surgery, craniofacial surgery and pediatric trauma. Per Clinical Trials.gov, pediatric trials have reported minimal adverse events as referenced in Appendix II. Some concerns exist about increased thrombotic events with the use of these agents, but large meta-analyses suggest that antifibrinolitics can be safely and efficaciously employed in pediatric patients.

